4.1. Overall Design

SURPASS-SWITCH is a Phase 4, randomized, open-label, active-controlled, parallel-group, multicenter, multinational trial to assess the efficacy and safety of tirzepatide 15 mg or MTD compared to dulaglutide 4.5 mg or MTD in participants with T2D.

This study will enroll participants with inadequately controlled T2D who are taking dulaglutide once weekly (0.75 mg or 1.5 mg) for at least 6 months prior to Visit 1, with or without (up to 3) background OAMs.

The maximum duration of study participation is approximately 47 weeks. This study includes

- an approximate 3-week screening period
- a 40-week treatment period, and
- a 4-week safety follow-up period.

See the SoA (Section 1.3) for additional details about the study periods and visit-specific assessments, including assessments needed at an ED visit.

Participants will be randomly assigned 1:1 to either

- continue with and escalate dulaglutide to 4.5 mg or MTD, or
- tirzepatide 15 mg or MTD.

Participants who are randomly assigned to tirzepatide will discontinue dulaglutide and initiate tirzepatide within 3 days of their next scheduled dose. The starting dose for tirzepatide is 2.5 mg once weekly for 4 weeks, escalated in 2.5-mg increments every 4 weeks until 15 mg or MTD is achieved, as described in Section 6.1.1.

4.1.1. Design Outline

Period I: Screening

Visit 1

Interested individuals will sign the ICF prior to initiating any procedure.

The investigator will review medical history and other inclusion and exclusion criteria prior to any diagnostic procedures. If the participant is eligible after this review, then the site will perform the diagnostic procedures detailed in the SoA to confirm eligibility.

Visit 2

The investigator will review the results of the screening laboratory measures to further assess participant eligibility.

For participants meeting all other eligibility requirements, a dilated fundoscopic examination will be scheduled and completed between Visit 2 and Visit 3.

Participants or caregivers, if applicable, will receive a BG meter and COA device.

Participants and their caregiver(s), if applicable, will receive training on

- COA device, including the eDiary data collection and the electronic PRO data collection
- diabetes self-monitoring and management, including instructions on diet and exercise, education about the signs, symptoms, and treatment of hypoglycemia and hyperglycemia
- recording blood glucose measurements, and
- study requirements.

Participants will be asked to monitor 7-point SMBG profiles (prior to and 2 hours after the 3 main meals and at bedtime) on 2 nonconsecutive days during the 2 weeks preceding prespecified visits, as shown in the SoA (Section 1.3).

At investigator's and participant's discretion, participants should monitor BG any time a hypoglycemic event is suspected or unusual symptoms are present. Additional measurements may be used to monitor trends in BG.

Participants should continue their diet and exercise routine and must not use any glucose-lowering treatment other than the OAM taken prior to the screening visit and should not change their dose or formulation.

Period II: Treatment Period

Visit 3 (Randomization)

See Section 6.1 for intervention details, and Section 6.3 for randomization and stratification factors.

All screening laboratory test results and screening dilated fundoscopic examination results must be reviewed for exclusion criteria prior to randomization and dosing at V3.

This is the general flow for Visit 3:

- Participants arrive to the clinic in the fasting state
- Study personnel confirm enrollment criteria
- Participants are randomly assigned to an intervention group
- Participants complete PRO questionnaires before any other study procedures if the participant is not adversely affected by the fasting condition or complete after the participant has sufficiently recovered
- Study personnel complete all required visit procedures, including the collection of vital signs, all baseline procedures, sample collection, and dispense study intervention
- Participants self-administer study intervention at home. Administration should occur on the day (± 3 days) of when the next dulaglutide administration is planned

Study intervention training

Participants who are randomly assigned to tirzepatide will receive appropriate training on using the device.

Participants who are randomly assigned to continue on dulaglutide may be trained at the participant's request.

In addition, study personnel will provide product-specific "instructions for use" information to the participants upon request.

Visit 4 through Visit 10

Participants complete all visit procedures described in the SoA.

Visit 11 or ED visit

Participants complete all visit procedures as described in the SoA.

Participants unable or unwilling to continue the study for any reason will perform an ED visit. If the participant is discontinuing during an unscheduled visit or a scheduled visit, that visit should be performed as the ED visit.

The investigator will determine a participant's transition from study treatment to another antihyperglycemic treatment plan.

Period III: Safety follow-up visit***Visit 801***

All participants who complete the treatment period or discontinue the study early (ED) are required to complete Visit 801, a safety follow-up visit, approximately 4 weeks after their last treatment or ED visit.

Participants complete all visit procedures as described in the SoA. Participants will return study eDiaries to the study site.

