Visit interval tolerance (days)			±3	±7	±3	±3	±3	±3	±3	±3	±7	±7	—	±7	
Fasting visit			X	X	X	X	X	X	X	X	X	X	X		
Remind participants about 7-point SMBG		X									X				Remind participant to monitor 7-point SMBG profiles (prior to and 2 hrs after the 3 main meals and at bedtime) on 2 nonconsecutive days during the 2 weeks preceding the specified visits.
Review 7-point SMBG values collected in the diary			X									X			
Review hypoglycemic events collected in the diary			X	X	X	X	X	X	X	X	X	X	X	X	
Participant Diary (Electronic)															
Participant diary dispensed		X													eDiary includes SMBG values, collection of intervention administration information on dosing days, and hypoglycemia.
Diary compliance check			X	X	X	X	X	X	X	X	X	X	X	X	
Diary return												X	X		

Study I8F-MC-GPIH	Period I - Screening		Period II- Treatment Period											Period III- Post-treatment Follow-up	Comments
			1	2	3	4	5	6	7	8	9	10	11	ED	
Visits														801	ED = early discontinuation
Weeks from randomization	-3	-2	0	4	8	12	16	20	24	32	40	—	—	4 weeks after the last dose	
Visit interval tolerance (days)			±3	±7	±3	±3	±3	±3	±3	±3	±7	±7	—	±7	
Fasting visit			X	X	X	X	X	X	X	X	X	X	X	X	
Patient-Reported Outcomes (Electronic)															
Complete prior to any clinical assessments															
Impact of Weight on Self-Perception (IW-SP)			X										X	X	Complete PROs before any other study procedures if the participant is not adversely affected by the fasting condition or after the participant has sufficiently recovered from the preceding visit procedures. Must be completed on eCOA device.
Ability to Perform Physical Activities of Daily Living (APPADL)			X										X	X	
Impact of Weight on Quality of Life-Lite-Clinical Trials Version (IWQOL-Lite-CT)			X										X	X	
Emotional Impact of Diabetes Treatment Questionnaire – Comparison (EIDTQc)													X	X	
Global Impression of Emotional Health (1 week recall)			X										X	X	
Global Impression of Emotional Health (since study start recall)													X	X	
Laboratory Tests and Sample Collections															
Hematology	X												X	X	
Hemoglobin A1c (HbA1c)	X		X	X	X	X	X	X	X	X	X	X	X	X	
Clinical chemistry	X		X						X		X	X	X	X	
Glucose	X		X	X	X	X	X	X	X	X	X	X	X	X	
Lipid panel			X						X		X	X	X	X	
Serum pregnancy	X														Only for WOCBP and females with a history of tubal ligation. See Section 10.4.

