Study I8F-MC-GPIH	Period I - Screening		Period II- Treatment Period											Period III- Post-treatment Follow-up	Comments		
			1	2	3	4	5	6	7	8	9	10	11	ED			
Visits															801	ED = early discontinuation	
Weeks from randomization	-3	-2	0	4	8	12	16	20	24	32	40	—	—	4 weeks after the last dose			
Visit interval tolerance (days)			±3	±7	±3	±3	±3	±3	±3	±3	±7	±7	—	±7			
Fasting visit				X	X	X	X	X	X	X	X	X	X				
Urine pregnancy (local)				X										X	X	Collect for WOCBP. Perform additional pregnancy tests, beyond those required per the SoA, at any time during the study if a menstrual period is missed, there is clinical suspicion of pregnancy, or as required by local law or regulation.	
Follicle-stimulating hormone (FSH)	X															Optional. Perform as needed to confirm postmenopausal status. See Section 10.4.	
Calcitonin	X													X	X	X	
Pancreatic amylase	X									X				X	X	X	
Lipase	X								X					X	X	X	
Cystatin C	X													X	X	X	
Estimated glomerular filtration rate (eGFR)	X													X	X	X	Calculate using CKD-EPI method.
Urinary albumin/creatinine ratio (UACR)	X													X	X	X	
Anti-GAD antibodies	X																
Randomization and Dosing using IWRS																	
Register visit	X	X	X	X	X	X	X	X	X	X	X	X	X	X	X		
Randomization			X														
Dispense study intervention				X	X	X	X	X	X	X	X	X				Self-administration of study intervention will be done at home and should occur on the day (±3 days) of when the next dulaglutide administration is planned.	

Study I8F-MC-GPIH	Period I - Screening		Period II- Treatment Period											Period III- Post-treatment Follow-up	Comments
			1	2	3	4	5	6	7	8	9	10	11	ED	
Visits														801	ED = early discontinuation
Weeks from randomization	-3	-2	0	4	8	12	16	20	24	32	40	—	—	4 weeks after the last dose	
Visit interval tolerance (days)			±3	±7	±3	±3	±3	±3	±3	±3	±7	±7	—	±7	
Fasting visit				X	X	X	X	X	X	X	X	X	X	X	
Dispense ancillary supplies				X	X	X	X	X	X	X	X	X	X	X	
Participant returns unused study intervention and ancillary supplies				X	X	X	X	X	X	X	X	X	X	X	
Assess study intervention compliance				X	X	X	X	X	X	X	X	X	X	X	

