6.3. Measures to Minimize Bias: Randomization and Blinding

Randomization

All participants will be centrally assigned through block randomization with a block size of 2 using an IWRS. Before the study is initiated, the login information and directions for the IWRS will be provided to each site.

Participants will be randomly assigned in a 1:1 ratio to tirzepatide or dose escalation of dulaglutide.

Participants will be stratified based on

- starting dulaglutide dose at Screening (0.75 mg, 1.5 mg)
- region (NA, EU)
- number of OAM (0-1 or 2-3), and
- HbA1c ($\leq 8.5\%$ or $> 8.5\%$).

Blinding

This is an open-label study.

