7.3. Lost to Follow-up

A participant will be considered lost to follow-up if he or she repeatedly fails to return for scheduled visits and is unable to be contacted by the study site. Site personnel or designee are expected to make diligent attempts to contact participants who fail to return for a scheduled visit or were otherwise unable to be followed up by the site.

8. Study Assessments and Procedures

Study procedures and their timing are summarized in the SoA.

Immediate safety concerns should be discussed with the sponsor immediately upon occurrence or awareness to determine if the participant should continue or discontinue study intervention.

Adherence to the study design requirements, including those specified in the SoA, is essential and required for study conduct.

All screening evaluations must be completed and reviewed to confirm that potential participants meet all eligibility criteria. The investigator will maintain a screening log to record details of all participants screened and to confirm eligibility or record reasons for screening failure, as applicable.

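### Visit 3 lists randomisation ahead of the baseline PROs in an open-label trial, and nothing clearly secures those PROs before the participant can know the arm

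*Protocol*

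**What the plan says.** Protocol 4.1.1 gives a general flow for Visit 3 as a bulleted list. The participant arrives fasting and staff confirm the enrolment criteria. Then come, in this order:

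- the allocation step: "Participants are randomly assigned to an intervention group"
- directly after it, the PRO step: "Participants complete PRO questionnaires before any other study procedures if the participant is not adversely affected by the fasting condition", with later completion allowed once the participant has recovered
- vital signs, baseline procedures, samples and dispensing
- "Participants self-administer study intervention at home"

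SAP 1.2 repeats the list in the same order.

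The Schedule of Activities (SoA, Protocol 1.3) heads the PRO block "Complete prior to any clinical assessments". Its comment column repeats the PRO rule and words the exception as completion "after the participant has sufficiently recovered from the preceding visit procedures". Randomisation is a separate SoA row, under "Randomization and Dosing using IWRS". The opening of Protocol Section 8 states: "Study procedures and their timing are summarized in the SoA". On blinding, Protocol 6.3 says: "This is an open-label study".

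Baseline (Protocol 9.3.1, SAP 4.1) is the last available value up to and including the randomisation visit, provided it precedes the first dose. The SoA first schedules the PROs at Visit 3.

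**The concern.** PROs are subjective. A participant who already knows whether they will switch drug or stay on dulaglutide may answer questions on physical function, self-perception or emotional health differently. A baseline is meant to be free of the allocation. If it is not, a difference between arms that arises from learning the allocation is treated as a pre-treatment characteristic and is adjusted for.

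A site that works down the Visit 3 list, or that uses the fasting exception, could collect the baseline PROs after the arm is known. Nothing later in the plan would pick this up, and no screening PRO could replace the value.

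**Working it through.** The documents give no figure to reproduce here. The check sets the texts side by side and then works out how a shifted baseline would reach the estimate.

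**1. Order in the lists.** Both lists give: arrival, eligibility, randomisation, PROs, other procedures and dispensing, home dosing. The bullets are unnumbered, but they run in time order from arrival to home dosing.

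**2. Two readings of the PRO rule.**

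- *Wide reading.* Section 8 says study procedures are summarised in the SoA, and randomisation is an SoA row. The PROs then belong before randomisation, and the list order says otherwise.
- *Narrow reading.* The rule covers only the procedures in the next bullet. Rule and list then agree, but completing the baseline PROs after randomisation becomes the planned sequence.

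The SoA block heading does not decide between them, because it speaks of clinical assessments and does not name randomisation.

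**3. The exception.** The Protocol 4.1.1 version allows completion after recovery. The SoA version speaks of recovery from visit procedures already done. Neither sets a limit at randomisation or at disclosure of the arm, so the exception can only move the PROs later.

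**4. The baseline definition.** It is bounded by the randomisation visit and the first dose, and that dose is taken at home after the visit. A PRO answered after randomisation at Visit 3 therefore qualifies as baseline.

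**5. Scope.** The PRO scores analysed are IWQOL-Lite-CT Physical Functioning, Total, Physical and Psychosocial, IW-SP, APPADL, GIEH 1-week recall, EIDTQc and GIEH since study start: 9 in all. EIDTQc and GIEH since study start have no baseline, so 9 - 2 = 7 are exposed.

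- One is an additional secondary measure: Physical Functioning. SAP Table 2 holds 3 HbA1c targets + 3 weight-loss targets + 1 composite + fasting serum glucose + waist circumference + BMI + Physical Functioning = 11 measures, so this is 1 of 11.
- The other six are exploratory (SAP Table 3).

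SAP 4.4.2 and 4.5 place none of the seven under type 1 error control.

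**6. How a shift would carry through.** SAP Tables 2 and 3 assign these scores an ANCOVA on change from baseline, with the baseline score as covariate. Assume that knowing the arm moves mean baseline in one arm by d points relative to the other, that the shift is constant within that arm, and that the Week 40 score is unchanged. Let D be the Week 40 difference between arms, E the baseline difference without the shift, and b the within-arm slope of the Week 40 score on baseline.

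- Unadjusted change difference: D - (E + d), a bias of -d.
- ANCOVA on change: the slope of change on baseline is b - 1, so the estimate is D - (E + d) - (b - 1)(E + d) = D - b(E + d), a bias of -b*d.

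The planned ANCOVA therefore carries only the fraction b of the shift. For b between 0 and 1 the size of the bias lies between 0 and the size of d. The documents give neither d nor b.

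**The case against.** **The conflict is not proven.** A reader might infer that the plan contradicts itself outright. It need not. Section 8 says procedures are summarised in the SoA; it does not say that every SoA row is a procedure in the sense of the PRO rule. Confirmation of eligibility is also an SoA row at Visit 3, and the list puts it ahead of the PROs as well. If every row counted, the PROs would have to precede that step too. The narrow reading is coherent and fits the SoA block heading. This objection stands, so no definite contradiction is claimed. It does not remove the concern, because on the narrow reading the baseline PROs are planned for after allocation.

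**Knowledge of the arm is not certain.** A reader might also infer that participants will answer with the arm known. The documents do not say when the participant is told. Allocation is central, through the IWRS, and dispensing, the first listed step that necessarily reveals the arm, comes after the PROs. This stands too: knowledge of the arm is possible, not established. But no text found withholds the arm until the PROs are done, and PROs delayed for recovery could fall after dispensing.

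**Little is at stake.** The endpoints are additional secondary or exploratory, and the Week 40 PROs are open-label whatever the order. Both statements are correct. The Week 40 part comes with the design; the baseline part is avoidable.

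**Conclusion.** The point holds as a minor gap in the plan. Randomisation is listed before the baseline PROs in an open-label trial, and neither the PRO rule, the exception nor the baseline definition clearly secures those answers before the participant can know the arm.

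Its scope is limited to the seven scores counted above. The primary HbA1c result, the key secondary weight result and type 1 error control are not affected.

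No size or direction of bias can be stated, and it may be zero. The -b*d expression rests on the assumptions given with it and shows only the route. The documents also do not say how many participants would answer late. They therefore do not support a claim that the PRO comparisons are biased by any particular amount.

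**What to change.** In both lists (Protocol 4.1.1 and SAP 1.2), move PRO completion ahead of randomisation. State there, and in the SoA PRO comment for Visit 3, that baseline PROs are completed before IWRS randomisation, or at least before the arm is disclosed to the participant. Say expressly that this includes PROs delayed for recovery from fasting.

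Keep the baseline definition as it is. Tightening it would leave late completers without a baseline and remove them from the planned ANCOVA.

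The cost is a small protocol wording amendment with IRB/IEC approval (Protocol 10.1.1), the same edit in the SAP, and possibly a short wait within Visit 3 for a participant who is recovering. The change removes only the baseline part of the problem; the Week 40 answers stay open-label.

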4.2. Scientific Rationale for Study Design

This study is designed to investigate the efficacy and safety of switching once weekly dulaglutide 0.75 mg or 1.5 mg to once weekly tirzepatide 15 mg or MTD, or continuing and escalating dulaglutide 4.5 mg or MTD in adults with T2D who are currently on a nonmaximal, stable dose of dulaglutide QW. Data from this study will show whether switching treatment from weekly dulaglutide to tirzepatide rather than intensifying the dulaglutide dose provides additional efficacy in adults with T2D.

Primary endpoint

HbA1c was chosen as the primary endpoint because it is an accepted and well-understood endpoint reflecting glycemic control over extended periods of time.

Duration of treatment period and posttreatment follow-up

The planned treatment duration of 40 weeks is appropriate to assess the effects and benefit/risk of tirzepatide 15 mg or MTD and dulaglutide 4.5 mg or MTD on glycemic control, weight, and potentially other clinically relevant outcomes.

Open-label design

An open-label design is used for this study to enable dose escalation and modification.

Choice of comparator

Once weekly dulaglutide was chosen as the active comparator because it is one of the most widely used weekly GLP-1 RAs.

Parallel-group design

The parallel-group design for treatment comparison was chosen to avoid any interaction between treatments that may interfere with the interpretation of the study outcome.

Demographics collection

In this study, collection of demographic information includes race and ethnicity, where permissible. The scientific rationale is based on the need to assess variable response in safety and/or efficacy based on race or ethnicity. This question can be answered only if all the relevant data are collected.

4.3. Justification for Dose

Tirzepatide doses

Tirzepatide 15 mg or MTD administered subcutaneously QW will be evaluated in this study.

The doses and associated escalation scheme were selected based on the results of global registrational Phase 3 studies in people with T2D. The requirement to escalate dose to 15 mg or MTD is based on the finding that tirzepatide lowers blood glucose and provides other metabolic benefits, including weight loss and lipid improvements in a dose-dependent manner.

Dose escalation

Tirzepatide

To mitigate the potential occurrence of GI AEs associated with tirzepatide and permit time for the development of tolerance to GI effects, a dose escalation scheme will be used in the tirzepatide arm. The treatment starts at a dose of 2.5 mg QW for 4 weeks and then escalates by 2.5-mg increments every 4 weeks until the 15-mg dose or maximum tolerated dose is reached (Section 6.1.1).

Dulaglutide

Dulaglutide will be escalated until the 4.5-mg dose or MTD is reached. For participants starting at 0.75 mg, dulaglutide will be escalated to 1.5 mg for 4 weeks, followed by 3.0 mg for another 4 weeks and then to 4.5 mg or MTD. For those starting at 1.5 mg, dulaglutide will be escalated to 3.0 mg for 4 weeks and then to 4.5 mg or MTD.

4.4. End of Study Definition

The end of the study is defined as the date of last scheduled procedure shown in the SoA for the last participant in the study globally.

A participant is considered to have completed the study if the participant has completed all periods of the study including the last visit or the last scheduled procedure shown in the SoA.

5. Study Population

Prospective approval of protocol deviations to recruitment and enrollment criteria, also known as protocol waivers or exemptions, is not permitted.

5.1. Inclusion Criteria

Participants are eligible to be included in the study only if all of the following criteria apply:

Age

1. Are 18 years old or of an acceptable age to provide informed consent according to local regulations, whichever is older.

Type of participant and disease characteristics

2. Have been diagnosed with T2D based on the World Health Organization classification or other locally applicable diagnostic standards.
3. Have HbA1c $\geq 7.0\%$ (≥ 53 mmol/mol) to $\leq 9.5\%$ (≤ 80 mmol/mol), as determined by the central laboratory at Visit 1.
4. Are currently on a stable dose of dulaglutide weekly (0.75 mg or 1.5 mg) for at least 6 months prior to Visit 1.
5. No treatment with OAM, or on a stable dose of up to 3 OAMs, which may include metformin, SGLT-2i, and/or sulfonylurea, for at least 3 months before Visit 1.

Weight

6. Have had stable body weight ($\pm 5\%$) during the 90 days preceding screening and agree to not initiate a diet and/or exercise program during the study with the intent of reducing body weight other than the lifestyle and dietary measures for diabetes treatment.
7. Have BMI ≥ 25 kg/m² at Visit 1.

Contraceptive/barrier requirements

8. Contraceptive use by participants should be consistent with local regulations regarding the methods of contraception for those participating in clinical studies.
 - Males may participate in this trial.
Please refer to Section 10.4 for additional guidance related to contraception.
 - WOCBP and women not of childbearing potential may participate in the study.
See Section 10.4 for definitions and additional requirements related to contraception.

Informed consent

9. Capable of giving signed informed consent as described in Section 10.1.3, Appendix 1, which includes compliance with the requirements and restrictions listed in the ICF and in this protocol.

Other inclusions

10. Are reliable and willing to make themselves available for the duration of the study and are willing and able to follow study procedures as required, including, but not limited to
 - self-injecting intervention or injection by a caregiver when applicable
 - willing to be assigned to a different injectable at randomization
 - taking provided study interventions as directed
 - maintaining an eDiary, and
 - completing electronic patient-reported questionnaires.

